7.10	Consent provisions for collection and use of participant data and biological specimens....	15
8.	ETHICAL AND REGULATORY CONSIDERATIONS	15
8.1	Assessment and management of risk	15
8.2	Research Ethics Committee (REC) and other Regulatory review & reports.....	16
8.3	Regulatory Review & Compliance	16
8.4	Amendments.....	16
8.5	Peer review	16
8.6	Patient & Public Involvement.....	16
8.7	Protocol compliance.....	16
8.8	Data protection and patient confidentiality	17
8.9	Indemnity	17
8.10	Access to the final study dataset.....	17
9.	DISSEMINATION POLICY	17
9.1	Dissemination policy	17
9.2	Authorship eligibility guidelines and any intended use of professional writers	18
9.3	Archiving Arrangements.....	18
10.	REFERENCES	19
11	APPENDICES.....	20
	Appendix 1 – Amendment History	20

KEY STUDY CONTACTS

Chief Investigator	
[name], Orthotics Department, Royal National Orthopaedic Hospital NHS Trust (RNOH), [name] [contact] [name] [contact]

Study Co-ordinator	
[name], Physiotherapist, Physiotherapy Department, RNOH [contact] [name]

Sponsor	
[name] Research & Innovation Centre, Royal National Orthopaedic Hospital NHS Trust, [name] [contact]

Joint-sponsor(s)/co-sponsor(s)	n/a
Funder(s)	n/a
Key Protocol Contributors	Details as above
Committees	n/a

STUDY SUMMARY

Study Title	A single centre, feasibility study using Dynamic Lycra Garments to address pain and instability associated with Hip Dysplasia
Internal ref. no. (or short title)	Dynamic Lycra Garments for hip dysplasia
Study Design	Feasibility/pilot study. Prospective, non-blinded, non-controlled. Single Centre.
Study Participants	Consenting patients receiving standard care + dynamic lycra garment intervention
Planned Size of Sample (if applicable)	8-12
Follow up duration (if applicable)	12 weeks
Planned Study Period	1 year October 2025 – 1 October 2026
Research Question/Aim(s)	The research question underpinning the project is as follows, "Can the use of dynamic compression shorts during daily

	
activities improve short term treatment outcomes in hip dysplasia patients?”.
 
This feasibility study will assess prevalence of hip dysplasia and hypermobility, refine the research protocol and measures, identify any complications of garment use, establish compliance and feedback on aspects of experience; gathering early evidence of effect and establish potential for future interventional study.
 
The intention of this study is primarily to establish the practicality of studying these effect of the garments over the period of a study, gather the opinions of patients and thereby allow us to assess the justification for further quantitative study, rather than the adjunctive effect of the shorts themselves.
 
The findings will inform the development of a study design which can more fully establish the generalisable degree to which this intervention can deliver effective relief from pain and disability for patients with hypermobility and hip dysplasia.

--	---

FUNDING AND SUPPORT IN KIND	
FUNDER(S) (Names and contact details of ALL organisations providing funding and/or support in kind for this study)	A feasibility study to be undertaken with in house funding at this stage.

ROLE OF STUDY SPONSOR AND FUNDER

The study sponsor retains management of the study design, conduct, data analysis and interpretation, manuscript writing, and dissemination of results and controls the final decision regarding any of these aspects of the study.

ROLES AND RESPONSIBILITIES OF STUDY MANAGEMENT COMMITTEES/GROUPS & INDIVIDUALS

This is a feasibility study.

PROTOCOL CONTRIBUTORS

The research team (CI, PI) assume responsibility for the study design, conduct, data analysis and interpretation, manuscript writing, and dissemination of results.

The sponsor controls the final decision regarding any of these aspects of the study.

[figure not shown]
A goal of this study is to gain informed feedback and opinion from members of the patient group of interest.

KEY WORDS:

Hip Dysplasia
Hypermobility
Ehlers Danlos Syndrome
Dynamic lycra garments
Orthotics
Physiotherapy

STUDY FLOW CHART

Fig 1: Patient information flowchart outlining the hip lycra garment study procedures. Participants may withdraw consent and exit the study at any point, without giving a reason.

ABBREVIATIONS	
AE	Adverse Event
AR	Adverse Reaction
CI	Chief Investigator
CRF	Case Report Form
DDH	Developmental Dysplasia of the Hip
DLS	Dynamic Lycra Shorts
GCP	Good Clinical Practice
GP	General Practitioner
HRA	Health Research Authority
ICF	Informed Consent Form
ISF	Investigator Site File
NHS	National Health Service
NIHR	National Institute for Health Research
PI	Principal Investigator
REC	Research Ethics Committee
RNOH	Royal National Orthopaedic Hospital NHS Trust
SAE	Serious Adverse Event

STUDY PROTOCOL

A single centre, feasibility study using Dynamic Lycra Garments to address pain and instability associated with Hip Dysplasia.

1. BACKGROUND

Muscle-tendon-related pain exists in about half of patients with hip dysplasia (DDH), the condition where the hip socket doesn't fully cover the ball portion of the upper thighbone, affecting patients' self-reported hip disability and muscle strength negatively (Jacobsen JS et al 2018). DDH has long been known to be a risk factor for pain and degenerative changes in the hip joint (Wilkin et al 2017). A strong association between hypermobility and DDH in adults has been shown (Santore et al 2020).

Joint proprioceptive deficit is documented in a variety of musculoskeletal conditions including osteoarthritis, ligament and meniscal injuries, and individuals with increased joint hypermobility, such as those with Ehlers-Danlos Syndrome (EDS). A meta-analysis finding concluded that lower limb joint proprioception is reduced in those with benign joint hypermobility syndrome (BJHS) compared to non-BJHS cohort (Smith et al 2013).

Conservative treatment methodologies are important in addressing hip pain (Ladurner 2021). Lycra garments are deployed in rehabilitation and high-performance populations, the therapeutic effects of which are thought to arise from neurophysiological modulation of muscle tone, prolonged stretch to shortened muscles; mechanical dampening down of excessive, inefficient movement; supporting unstable areas of the body; and enhancing sensory feedback (Snowdon et al 2018).

Postural correction has been shown to reduce hip pain in adult with acetabular dysplasia (Lewis et al 2015) while lycra orthoses have reduced pain and improved stability in the shoulder (Matthews et al 2015) and in the hip (Higo et al 2023). A range of primary and secondary outcome measures were deployed to show that, in a 4 week duration randomised control trial (RCT) of compression garments on EDS patient shoulder stability there was high satisfaction with improvement in focal pain, stability and function along with objectively measured high-speed power development, albeit with no significant carry over effect (Chaléat-Valayer et al, 2002).

In summary it is possible that, in patients living with both DDH and joint hypermobility dynamic lycra shorts (DLS) could be beneficial in reducing pain associated with posture and physical activity. The existing evidence to justify use in this population currently lacks both quality and strength.

2. RATIONALE

It is envisaged that the long-term aim of clinical trials programme by the research team will be to establish a generalizable evidence base for/against the use of lycra compression shorts to improve treatment outcomes in these populations. However, the scope of the current proposed feasibility study is limited to testing of the pathway and research protocol, participant adherence and feedback and gather early evidence of effect size, power calculation and to guide decision making as to whether this intervention is appropriate for further study and underpin funding applications (commercial/academic partners).

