5. STUDY DESIGN, METHODS OF DATA COLLECTION AND DATA ANALYSIS

This prospective, 2 x repeated measures, non-blinded, non-controlled study will invite a cohort of patients to take part in a study that combines usual care with adjunctive use of DLS for a limited period of 8-12 weeks, in accord with the Declaration of Helsinki.

The null hypothesis in relation to the primary outcome measure can be stated as follows: 'use of dynamic compression shorts during daily activities does not modify the degree of pain experienced by hip dysplasia patients.'

Protocol: Patient screened by the clinical care team, will be invited to participate by the medical team, based upon the inclusion and exclusion criteria specified. They will be provided with an information sheet (PIS). The medical team will pass the prospect's details to the research team who will subsequently make contact to invite to the initial, face to face baseline session. If the patient for any or no reason declines to continue at this or any point, they will continue on the standard treatment pathway.

Recruitment session: If the patient agrees to attend, they will attend at the research site. The researcher will affirm that the prospects have read and understood the PIS information. Written consent will be sought and witnessed. Hypermobility status will be evaluated. The shorts will be measured (a single circumferential tape measure at the level of the anterior superior iliac crests (ASIS)). The participant will complete a HADS 10 evaluation form. Following the session the participant's GP will be sent a study notification letter.

The shorts have an order-to-delivery time of 2 weeks. Following delivery of these to the research site, the following activities will take place in sessions/intervals as follows

1. **Baseline session.** i. strength testing, questionnaires and interview completion. ii. shorts fitting and education, standardised method. Orthosis and exercise education will then be provided. The outcome measures gathered at baseline and followup will include: iHOT-12 questionnaire Orthotics Prosthetics Users Survey (OPUS) satisfaction subscales Hand Dynamometer - muscle strength by hip degree of movement.
Participants will be directed to wear the lycra shorts during all daily activity and physiotherapy exercise, where possible and diarise their experiences.

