2. **Intervention window.** During the 12 weeks home trial period each participant will complete a formatted daily exercise and lycra garment intervention diary. Participants will be provided with a support contact telephone/email. All contact will be fully summarised in the participant activity timeline log.]
3. **Follow up session:** strength testing, follow up and repeat OPUS questionnaires and interview. Participant debrief either during this session or as a follow up communication.

4. At the **study conclusion** each participant will be asked to complete an interview and receive a debrief of their personal study data. They will be asked to reflect upon their qualitative experience and perceived personal and generalisable benefits of current and planned research into such conservative therapies.

Data will be collected using paper Case Report Forms (CRFs) designed by the research teams and stored in locked cabinets within the clinical facility.

The scores from the validated questionnaires, patient diaries and comments recorded at follow-up will be digitised and recorded on secure databases. As is appropriate in a small-scale study, quantitative results will be considered as descriptives such as mean, median, mode, percentage, frequency, skewness, and range. Qualitative data will be evaluated by analysing the content for systematic themes, patterns and features in participant experience.

All databases used during the study will be on password and firewall protected, NHS Trust proprietary systems and private cloud channels accessible only the research team.

Participant-specific study records will be anonymised by coding, with administrative decoding under the control of Principal Investigator (PI) only, in accordance with the NHS Code of Practice for Confidentiality.

Where hard copy records or questionnaires are generated during the study, these will be scanned electronically, and the hard copies will be destroyed. Research data will be stored on password protected Trust systems and accessible only by the research team.

Research data will be stored for 5 years following completion of the study. Personal data will be stored and accessed for the limited period of 12 months.

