7. SAMPLE AND RECRUITMENT

7.1 Eligibility Criteria

Current treatment pathway, for hip dysplasia patients who are deemed appropriate for conservative treatment, is to be referred by the medical team to the Principal Investigator (PI) who triages all referrals. The PI is also the researcher responsible for executing the participant-facing research protocol. During the triage referrals the PI will identify and tag those prospective participants (prospects) who might be appropriate for inclusion. All patients attend a pre-treatment assessment appointment. During this

appointment, additional time will be allocated to discuss the study topic, pre-screen the prospects and issue the PIS if appropriate. Prospective participants will be given at least 24 hours to read the PIS and consider their participation in the study. Should the prospect signal their consent, they will be invited by the PI to a study baseline session where they will be given the opportunity to ask any questions. If they are happy to take part, informed, written consent will be gained.

This is a single cohort study.

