7.5 Size of sample

8-12, commensurate with the available population and the pilot/feasibility study design.

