7.8 Participant identification

A member of the patient's existing clinical care team will be reviewing the referral details as part of standard triage protocol. During this referral triage process the PI will identify and tag those prospective participants (prospects) who might be appropriate for inclusion.

All patients attend a pre-treatment assessment appointment. During this appointment, additional time will be allotted to discuss the study topic, screen the prospects and issue the PIS if appropriate.

Participants will receive no payment for taking part in the study. However, participants will be able to retain the lycra shorts for continued use following conclusion of the study if the device proves to deliver personal benefit. Although this could be considered as a non-financial incentive to take part, the item will be provided as a prescribed item.

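### Section 2 lists effect size and a power calculation as outputs, but an uncontrolled before-after change in 8-12 people who start shorts and exercise education together cannot estimate what the shorts add

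*Protocol*

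**What the plan says.** - **Aim.** Protocol section 2 puts within scope to "gather early evidence of effect size, power calculation", to inform the choice of whether to take the intervention further, and to support funding applications.
- **Hypothesis.** Section 4 asks whether the shorts improve short-term outcomes. Section 5 states a null hypothesis that using the shorts does not change pain.
- **Design.** Section 5: "This prospective, 2 x repeated measures, non-blinded, non-controlled study will invite a cohort of patients". Section 7.1: "This is a single cohort study".
- **Size.** Section 7.5: "8-12, commensurate with the available population and the pilot/feasibility study design". No significance level, power, SD or target difference is given.
- **Treatments.** At the baseline session the shorts are fitted and, in the same session, "Orthosis and exercise education will then be provided". Section 6 says standard treatment is given as well as the shorts. Section 3 describes the shorts as an addition to an approach built on exercise and education.
- **Limits the protocol sets itself.** The Study Summary and section 4.2 say the main intention is the practicality of studying the garments and the case for further work, not the added effect of the shorts. Section 4.2 nevertheless keeps early evidence of effect among the things to be gathered. Section 5 plans descriptive summaries only.

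**The concern.** Sections 3 and 4 look ahead to a randomised or comparative trial. That trial needs the effect of shorts plus usual care against usual care alone. This study has no group on usual care alone and no run-in on usual care before the shorts, so it never observes the second half of that comparison. A statistical analysis plan could add intervals or more summaries, but it could not create a comparator or separate two treatments begun at one visit.

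At stake is what the study may conclude. Section 2 ties effect size and power to the decision on further study and to funding bids. A reader of the final report could take the mean iHOT-12 change as the benefit of the shorts. The protocol invites that reading in sections 2, 4 and 5 and discourages it in the Study Summary and section 4.2.

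**Working it through.** **1. Nothing to reproduce.** The 8-12 rests on the available population and the pilot design, not on a calculation.

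**2. What the change measures.** For each participant the iHOT-12 is taken at baseline and follow-up. Then

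mean change = shorts + exercise and education + natural course + regression to the mean + expectation.

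The design gives one number for the sum. No sample size separates the first term from the rest.

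**3. Precision of the sum itself.** Inputs: n = 8 and n = 12 (section 7.5), all followed up. Half-width of the 95% interval for a mean change, in units of the SD of change: t(0.975, n-1)/√n.

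| n | t | half-width |
|---|---|---|
| 8 | 2.365 | 2.365/√8 = 0.84 SD |
| 12 | 2.201 | 2.201/√12 = 0.64 SD |

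By the noncentral t distribution, an observed standardised change of 0.5 would have a 95% interval of -0.25 to 1.22 (n=8) or -0.11 to 1.09 (n=12).

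**4. Precision of the SD.** 95% limits as multiples of the estimate: √((n-1)/χ²), with χ² at its 0.975 and 0.025 quantiles.

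- n=8: √(7/16.01) = 0.66 to √(7/1.690) = 2.04
- n=12: √(11/21.92) = 0.71 to √(11/3.816) = 1.70

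Required sample size goes with SD², so from this source alone it could be 0.44 to 4.14 times (n=8) or 0.50 to 2.88 times (n=12) the planned number. The SD is estimable here, but needs its interval beside it.

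**5. Consequence if the change were used for planning (illustration; the inputs are assumptions, not protocol figures).** Assume a 1:1 trial, two-sided 5%, 80% power, normal approximation, n per arm = 2(1.960 + 0.842)²/d². Suppose the whole change is d = 0.5 on the between-patient SD scale, so the plan is 15.70/0.25 = 63 per arm. Let a share s of the change be due to the shorts. The need is then 15.70/(0.5s)², and the power with 63 per arm is Φ(0.5s·√(63/2) - 1.960).

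| share s | true d | needed per arm | power with 63 per arm |
|---|---|---|---|
| 100% | 0.5 | 63 | 80% |
| 75% | 0.375 | 112 | 56% |
| 50% | 0.25 | 252 | 29% |
| 25% | 0.125 | 1005 | 10% |

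In general the planned number is about s² of the needed number, whatever the starting d. The documents give no value for s. The units in step 3 (SD of change) and step 5 (between-patient SD) agree only if the baseline-to-follow-up correlation is 0.5 and the SD is the same at both visits.

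**The case against.** The strongest reply is that the protocol already disclaims this use. The Study Summary and section 4.2 put practicality first and set aside the added effect, section 5 restricts results to descriptives, and uncontrolled feasibility cohorts are a legitimate choice. That stands as far as it goes: it would be wrong to say the study's main purpose is to estimate the effect of the shorts. But the disclaimer sits beside an aim in section 2, a phrase in 4.2 and a hypothesis in section 5 that say otherwise, so the protocol contradicts itself.

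Some stronger readings are tempting and are not supported:

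- *The next trial will be mis-sized.* No section says the change will be the target difference. The section 2 phrase is loosely built and could mean collecting variance inputs. The harm is conditional. Its direction is not certain for any single pilot either. In a simulation with no bias and a true standardised change of 0.5, 33% (n=8) or 28% (n=12) of pilots imply less than half the needed number, and 33% or 30% imply more than twice it or show no positive effect.
- *The planned analysis leaves out the SD.* Section 5 says "quantitative results will be considered as descriptives such as mean, median, mode, percentage, frequency, skewness, and range". The words introducing the list make it open, and the choice of summaries belongs to the analysis plan.
- *Participants keep the shorts only if they report benefit, so their scores are tilted.* Section 7.8 lets them "retain the lycra shorts for continued use following conclusion of the study if the device proves to deliver personal benefit". The word *only* is not there, and nothing links keeping the shorts to a study score.

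**Conclusion.** The point holds as a fault in what the protocol says it will deliver. The before-after change cannot estimate the added effect of the shorts, and this follows from the design alone, without any assumed figure. Its imprecision (0.84 SD at n=8, 0.64 SD at n=12) follows from the stated sample size with complete follow-up and the usual normal-theory interval; dropout would widen it.

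Under-sizing of a later trial follows only if two conditions are met: the change is taken as the planning difference, and usual care, time or expectation contributes improvement. The amount cannot be fixed from the documents. The table in the working shows how fast it grows under assumed shares and is not a forecast.

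**What to change.** 1. In section 2, replace the effect-size and power-calculation aim with a statement such as: *the before-after change is not an estimate of the effect of the shorts; it will not be used as the target difference of a later trial, nor as evidence of effect in deciding whether to proceed.*
2. Bring the section 4.2 wording on early evidence of effect and the section 5 null hypothesis into line with that statement and with the Study Summary.
3. Say what the study will supply: recruitment, retention, wear and outcome completeness, together with the iHOT-12 SD and the baseline-to-follow-up correlation, each with a confidence interval.
4. State that the target difference of the next trial will come from a justified minimally important difference.

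The cost is a wording amendment, with no added visit, form or participant. The downside is that the study can claim less, and the next trial may look larger when planned on this basis.

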3. THEORETICAL FRAMEWORK

The intervention, dynamic lycra shorts, are a made-to-order CE marked item which are marketed towards treating the symptoms of joint hypermobility amongst many other pathologies. No generalisable peer-reviewed evidence currently exists to support their treatment effectiveness in the current population of interest, as an adjunct to current approach which is based around exercise and education. Furthermore, qualitative aspects of use of these highly compressive lycra garments, such as impact on

self-care or comfort, that could negatively impact on sustained use have not been explored in the peer-reviewed literature. Before embarking upon a randomised trial it is important to confirm; the incidence of presentation of the target population, hypermobile DDH patients who are suitable for study inclusion.

- the fraction of whom are likely to consent and then choose to remain within the study protocol until the planned conclusion.
- extent of compliance with the intervention.
- identify aspects of the protocol that, through researcher and participant experience, may require modification.
- gain informed participant feedback as to the potential benefits of further research on this and similar topics.
- the incidence of anxiety and/or depression in the target population, which is thought to be common and could be an important variable in determining the outcome of treatment.

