7.2 Inclusion criteria

All patients passing through the RNOH Hip Unit, diagnosed with DDH suitable for conservative treatment with physiotherapy.

- Age 18 years or over.
- Both males and females.
- Able to attend the RNOH Stanmore site for in-person sessions.

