7.3 Exclusion criteria

- Less than 18 years of age.
- Diagnosed other musculoskeletal pathology affecting hips or pelvis
- Prior surgical intervention to treat a lower limb disease/disorder
- Unable to attend the RNOH Stanmore site for in-person sessions.

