7.9 Consent

All patients attend a pre-treatment assessment appointment. During this appointment, additional time will be allotted to discuss the study topic, screen the prospects, issue the PIS if appropriate and answer any questions the prospect may have.

Should the prospect signal their consent, they will be invited by the PI to a study baseline session where informed, written consent will be gained prior to any study activities being undertaken.

The Principal Investigator will take written consent.

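### The presentation rate and consent fraction promised for hypermobile DDH patients cannot be obtained, because hypermobility is recorded only in the 8-12 who consent and no referral log is specified

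*Protocol*

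**What the plan says.** The Study Summary (Research Question/Aim(s)) states: "This feasibility study will assess prevalence of hip dysplasia and hypermobility". Section 3 lists what must be confirmed before a randomised trial. The list opens with "the incidence of presentation of the target population, hypermobile DDH patients who are suitable for study inclusion" and continues with "the fraction of whom are likely to consent and then choose to remain within the study protocol until the planned conclusion". Both items refer to patients who have DDH and are hypermobile.

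The entry criteria are wider. Section 7.2 takes adults passing through the Hip Unit who are "diagnosed with DDH suitable for conservative treatment with physiotherapy". Hypermobility is named in neither 7.2 nor 7.3. Section 7.3 does exclude "Diagnosed other musculoskeletal pathology affecting hips or pelvis".

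On timing, the recruitment session in section 5 reads: "Written consent will be sought and witnessed. Hypermobility status will be evaluated". No instrument or cut-off is given. Section 7.9 adds that "informed, written consent will be gained prior to any study activities being undertaken". Before that, under sections 7.1, 7.4 and 7.6 to 7.8, the principal investigator triages referrals and tags those who may be suitable. Section 7.5 sets the sample at "8-12, commensurate with the available population and the pilot/feasibility study design".

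**The concern.** A presentation rate for hypermobile DDH patients needs a count of those patients among everyone referred over a known period. A consent fraction needs the number of hypermobile patients invited as its denominator. Under the protocol, hypermobility becomes known only once a patient has been tagged, approached and has consented, so both quantities lack the data that define them.

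At stake are the recruitment assumptions for the later trial. If that trial is to enrol hypermobile DDH patients, its planners need to know how many present and how many agree. These figures cannot readily be recovered after recruitment closes, and no analysis plan can supply a status that was never recorded.

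**Working it through.** **Promised quantities against planned data**

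| Quantity | Data needed | What the protocol collects |
|---|---|---|
| Prevalence of DDH | A group not selected on DDH | Only DDH patients can enter (7.2), so it is 100% by entry |
| Presentation rate of hypermobile DDH | Hypermobile patients among all DDH referrals in a fixed window | Status in consenters only (5, 7.9); no referral count specified |
| Consent fraction of hypermobile DDH | Hypermobile patients approached, and those who consent | The consenters only; status of decliners unknown |
| Retention of hypermobile DDH | Follow-up of hypermobile participants | Available, for however many happen to enter |
| Hypermobile share | Status in all presenting DDH patients | Share among consenters only |

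**The plan's own figure.** The sample of 8-12 is pragmatic. No precision, effect size or dropout is stated, so there is no calculation to reproduce.

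**Sampling error of the crude share.** The exact (Clopper-Pearson) 95% interval for x out of n runs from the 0.025 quantile of Beta(x, n-x+1) to the 0.975 quantile of Beta(x+1, n-x). The documents give no hypermobility rate, so a range is assumed:

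| Assumed share | n = 8 | n = 12 |
|---|---|---|
| 25% | 2/8: 3.2-65.1% | 3/12: 5.5-57.2% |
| 50% | 4/8: 15.7-84.3% | 6/12: 21.1-78.9% |
| 75% | 6/8: 34.9-96.8% | 9/12: 42.8-94.5% |

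**Number from the target group.** At an assumed 25%, the expected count is 8 × 0.25 = 2 or 12 × 0.25 = 3. The binomial chance of two or fewer is 68% at n = 8 and 39% at n = 12. At an assumed 50% the expected counts are 4 and 6, and the chances are 14.5% and 1.9%.

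**Selection.** Let p be the true share and RR the relative chance of being tagged and consenting if hypermobile. The observed share is then p·RR / (p·RR + 1 - p). With p = 0.50 and RR = 2 it is 1.00 / 1.50 = 67%. With RR = 0.5 it is 0.25 / 0.75 = 33%. RR is unknown and the design does not estimate it, so the direction of any bias is unknown too.

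**What a log would give.** For a 95% half-width h, n = 1.96² × p(1 - p) / h². At p = 0.50 this gives 97 referrals for h = 0.10 and 43 for h = 0.15. At p = 0.25 or 0.75 it gives 73 and 33. The protocol does not state the referral volume, so the precision a log would reach is also unknown.

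**The case against.** The best defence is that this is a small feasibility study with descriptive analysis, and that prevalence is not central to it. The scope in section 2, the objectives in 4.1 and the outcome statement in 4.2 all omit it. The title, research question and null hypothesis speak of hip dysplasia patients, which fits the open criterion in 7.2. This stands, and it limits the weight of the point: the protocol does not rank the presentation rate above compliance or feedback. Section 3 nevertheless lists it, with the consent fraction, as something to be confirmed before a trial. The complaint is about data that are not collected, and small numbers alone would not justify it.

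Four stronger readings are tempting, and the documents do not support them.

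- A reader might infer that nothing can be estimated. A crude hypermobile share among consenters can be computed. Since the principal investigator triages all these referrals, DDH presentations could also be counted. The protocol simply does not provide for that count, and the count alone would not give hypermobility status.
- A reader might infer that 7.3 shuts out the target group and biases the hypermobile share downwards. Its wording could be read to cover diagnosed Ehlers-Danlos syndrome or muscle-tendon pathology, which the Background says causes pain in about half of DDH patients. But Ehlers-Danlos syndrome and hypermobility are key words, and hypermobility is evaluated in participants. This is an ambiguity, not a demonstrated exclusion.
- A reader might treat the DDH prevalence aim as a serious failure. The phrase may mean the two conditions occurring together. It is loose wording, and no decision is shown to depend on it.
- A reader might think the remedy is only one more column in a log. Sections 7.9 and 7.10 put consent before study activities and require specific consent for access to notes. Recording hypermobility in people who have not consented needs a stated basis.

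**Conclusion.** The mismatch is real and should be settled before recruitment. As written, the study can describe hypermobility in 8-12 tagged, consenting patients. It cannot give a valid presentation rate or consent fraction for hypermobile DDH patients. DDH prevalence is fixed at 100% by entry.

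If half of participants were hypermobile, the crude share would carry an exact 95% interval of about 16-84% at n = 8 and 21-79% at n = 12, before any selection effect. Findings specific to the target group would rest on 4 to 6 people, or on 2 or 3 if the share were 25%. These shares are assumptions. The conclusion that the two figures cannot be obtained does not depend on them. It rests on status being recorded after consent and on no log being specified. It would soften if usual care already records hypermobility in all these patients, which the protocol does not say.

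**What to change.** - Keep an anonymous log of all consecutive DDH referrals triaged in the recruitment window, with counts referred, eligible, approached and consented.
- Add hypermobility status, by a named instrument and cut-off, at the pre-treatment assessment that all patients attend. Do this either as usual-care data or with its pre-consent recording covered in the REC submission, and reconcile it with 7.9 and 7.10.
- Report presentation rate, hypermobile share and consent fraction from that log, with exact intervals, and describe participants by hypermobility status. Subgroups will be small, so this should stay descriptive.
- If the recording is not approved, withdraw the incidence and consent-fraction aims for hypermobile patients.
- In either case, delete the prevalence of hip dysplasia as an aim and state the study population consistently as DDH.
- Reconcile the 7.3 exclusion of other hip or pelvic pathology with the hypermobility/Ehlers-Danlos focus and with the muscle-tendon pain described in the Background. Which patients are eligible is for the sponsor to decide.

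The cost is a simple log, a few minutes in an appointment where extra time is already set aside, and a change of ethics wording. The ethics change is the part that needs lead time.
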